## 5 PROCEDURES

**5.1 Study procedures.** Using lay language, provide a complete description of the study procedures, including the sequence, intervention or manipulation (if any), drug dosing information (if any), use of records, time required, and setting/location. If it is available and you think it would be helpful to the IRB: Upload a study flow sheet or table to the **Supporting Documents SmartForm** in **Zipline**.

*For studies comparing standards of care: It is important to accurately identify the research procedures. See UW IRB [POLICY: Risks of Harm from Standard Care](#) and the draft guidance from the federal Office of Human Research Protections, ["Guidance on Disclosing Reasonably Foreseeable Risks in Research Evaluating Standards of Care"](#), October 20, 2014.*

Aim 1:  
[redacted]

Aim 2:

Once a local health department has been recruited to participate in the study, they will be randomized to one of two conditions for the trial: 1) standard training and technical assistance or 2) standard training plus enhanced technical assistance.

Briefly, local health department staff will be trained to deliver the *Connect to Wellness* intervention to worksites that they recruit. In the Assessment phase, staff will measure current worksite implementation of physical activity, nutrition, cancer screening, and tobacco cessation evidence-based interventions (with the Baseline Employer Assessment Survey). [redacted] During the Implementation phase (months 3-12), the worksite begins adopting the recommended evidence-based intervention policies and programs and promoting them to workers. At the conclusion of the Implementation phase (month 12), the local health department staff will re-administer the Employer Assessment Survey. After this 12-month period, worksites are able to contact the local health department for technical assistance; the health department may also periodically contact worksites with study updates or to provide relevant materials or offer implementation support.

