3. We will adapt adoption, implementation, and maintenance items from the Prevention Program Assessment and ask local health department staff to complete these items at 12 and 24 months to assess their implementation and intent to maintain *Connect to Wellness*. The Program Sustainability Assessment Tool will be used as an additional measure to assess capacity to maintain *Connect to Wellness*.
4. Staff will be asked to track and provide data on the following: number of meetings, phone contacts, and e-mails with each worksite; number of worksites that complete *Connect to Wellness*; and personnel time, travel costs, and costs for printing materials for worksites.

In addition to the measures described above, local health department staff will provide us with the Employer Assessment Survey data that they collect from the worksites, which will further help us to determine which implementation strategy is more effective. The identities of the worksite representatives that we ask to complete the brief satisfaction survey will be known to us for recruitment purposes, but we will not retain this information as part of our study data. The identities of these representatives will not be known otherwise. For the employer assessment survey, we will only know the worksite name and corresponding ID number.

Lastly, the research team will track local health department's participation in *Connect to Wellness* training sessions and their attendance at technical assistance calls (group calls and one-on-one calls). The *Connect to Wellness* training and support website will track each local health department's log-ins, visits to the website, and material downloads.

For the worksite representatives, we will collect data on their satisfaction with *Connect to Wellness*.

**5.3 Data sources.** For all types of data that you will access or collect for this research: Identify whether you are obtaining the data from the subjects (or subjects' specimens) or whether you are obtaining the data from some other source (and identify the source).

*If you have already provided this information in Question 5.1, you do not need to repeat the information here.*

Aim 1:  
[redacted]

Aims 2/3:  
The data described above will come from members of the research team, local health department staff, and worksite representatives.

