
*\*\* If you checked the box about radio-isotopes: you are responsible for informing in advance all appropriate clinical personnel (e.g., nurses, technicians, anesthesiologists, surgeons) about the administration and use of the radio-isotope, to ensure that any personal safety issues (e.g., pregnancy) can be appropriately addressed. This is a condition of IRB approval.*

**10.5 Data and Safety Monitoring.** A Data and Safety Monitoring Plan (DSMP) is required for clinical trials (as defined by NIH). If required for your research, upload your DSMP to the **Supporting Documents** SmartForm in **Zipline**. If it is embedded in another document you are uploading (for example, a Study Protocol, use the text box below to name the document that has the DSMP.

N/A

**10.6 Un-blinding.** If this is a double-blinded or single-blinded study in which the participant and/or you do not know the group to which the participant is assigned: describe the circumstances under which un-blinding would be necessary, and to whom the un-blinded information would be provided.

N/A

**10.7 Withdrawal of participants.** If applicable, describe the anticipated circumstances under which participants will be withdrawn from the research without their consent. Also, describe any procedures for orderly withdrawal of a participant, regardless of the reason, including whether it will involve partial withdrawal from procedures and any intervention but continued data collection or long-term follow-up.

N/A

**10.8 Anticipated direct benefits to participants.** If there are any direct research-related benefits that some or all individual participants are likely to experience from taking part in the research, describe them below:

*Do not include benefits to society or others, and do not include subject payment (if any). Examples: medical benefits such as laboratory tests (if subjects receive the results); psychological resources made available to participants; training or education that is provided.*

Aim 1:  
[redacted]

Aims 2/3:

A potential benefit to local health departments is increased capacity to do worksite wellness activities. Worksites and their workers will potentially benefit from this research by creating healthier environments for their workers.

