3. We will adapt adoption, implementation, and maintenance items from the Prevention Program Assessment and ask local health department staff to complete these items at 12 and 24 months to assess their implementation and intent to maintain *Connect to Wellness*. The Program Sustainability Assessment Tool will be used as an additional measure to assess capacity to maintain *Connect to Wellness*.
4. Staff will be asked to track and provide data on the following: number of meetings, phone contacts, and e-mails with each worksite; number of worksites that complete *Connect to Wellness*; and personnel time, travel costs, and costs for printing materials for worksites.

In addition to the measures described above, local health department staff will provide us with the Employer Assessment Survey data that they collect from the worksites, which will further help us to determine which implementation strategy is more effective. The identities of the worksite representatives that we ask to complete the brief satisfaction survey will be known to us for recruitment purposes, but we will not retain this information as part of our study data. The identities of these representatives will not be known otherwise. For the employer assessment survey, we will only know the worksite name and corresponding ID number.

Lastly, the research team will track local health department's participation in *Connect to Wellness* training sessions and their attendance at technical assistance calls (group calls and one-on-one calls). The *Connect to Wellness* training and support website will track each local health department's log-ins, visits to the website, and material downloads.

For the worksite representatives, we will collect data on their satisfaction with *Connect to Wellness*.

**5.3 Data sources.** For all types of data that you will access or collect for this research: Identify whether you are obtaining the data from the subjects (or subjects' specimens) or whether you are obtaining the data from some other source (and identify the source).

If you have already provided this information in Question 5.1, you do not need to repeat the information here.

Aim 1:  
[redacted]

Aims 2/3:

The data described above will come from members of the research team, local health department staff, and worksite representatives.

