Study Identification

Unique protocol identification number: STUDY00004627

Brief Title: Training LHD's to disseminate evidence-based interventions to small work sites

Official Title: Training Local Health Departments to Disseminate Evidence-Based Interventions to Small and Low-Wage Worksites

Secondary IDs: 2R01CA160217 [U.S. NIH Grant/Contract Award Number]
NCI-2021-02876 [Registry ID: CTRP (Clinical Trial Reporting Program)]
RG1121453 [Fred Hutch/University of Washington Cancer Consortium]

Document date: June 28th, 2017

This document includes the statistical analysis plan excerpted from our grant proposal. We completed this text on the above date.

Statistical analysis plan

To test whether LHDs in the enhanced arm recruit more worksites than LHDs in the standard arm, we will use a generalized linear model with log link. Robust standard error will be performed to obtain valid test results, since we expect the number of worksites recruited to be overdispersed relative to the Poisson distribution. We will perform a secondary analysis to test whether the rate of recruitment increases over time and whether such an increase is modified by treatment status. To study the time effects, we will analyze the number of worksite recruitments in 6-month intervals. The estimation will be implemented using a generalized estimating equation with an autoregressive working correlation matrix of order 1. Robust standard error will be performed to obtain valid test results of correlated outcome data. We will use linear models to study the worksite implementation score. Since worksites are nested within LHDs, we will implement the estimation using generalized estimating equation with robust standard error.

Power analysis. Our first primary outcome is the number of worksites recruited by each LHD during the study period (24 months). Based on power analysis using the Washington State pilot data, we propose a sample size of 40 LHDs (20 per arm) for this study. The mean number of worksites recruited over a 12-month period was 8.4 (sd=4.4). The proposed design will have at least 80% power to detect a mean difference of 2.6 worksites per year between the two arms. Our second primary outcome is the worksite implementation score, collected 12 months after the initial delivery of *Connect to Wellness*. Based on the preliminary results of the parent project, our design has at least 80% power to detect a 6% difference in implementation scores between the two intervention groups.

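### The second primary analysis uses only worksites with a month-12 score and has no missing-data method, so loss that is related to the score and differs between arms would bias the comparison by an unknown amount in an unknown direction

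*SAP*

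**What the plan says.** The SAP (Power analysis paragraph) defines the endpoint: "Our second primary outcome is the worksite implementation score, collected 12 months after the initial delivery of" Connect to Wellness. The analysis paragraph says "We will use linear models to study the worksite implementation score" and continues: "Since worksites are nested within LHDs, we will implement the estimation using generalized estimating equation with robust standard error". It mentions no covariate, analysis set, weighting, imputation, attrition allowance or sensitivity analysis for this outcome.

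The protocol (Section 5.1, in both versions of the form) says who collects the score: "At the conclusion of the Implementation phase (month 12), the local health department staff will re-administer the Employer Assessment Survey". Section 5.2, item 4, asks staff to report the "number of worksites that complete" the programme, so some worksites are expected not to complete. The same item records the "number of meetings, phone contacts, and e-mails with each worksite". Section 5.1 gives one-on-one access and proactive monthly contact to health departments in the enhanced arm only. Section 10.7, where the form asks about withdrawal, "including whether it will involve partial withdrawal from procedures and any intervention but continued data collection or long-term follow-up", is answered N/A.

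**The concern.** Each worksite has one post-baseline value. If it is missing, the worksite drops out of this GEE altogether. Robust standard errors deal with clustering within health departments. They do nothing about which worksites supply a score.

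Worksites that disengage may well be poorer implementers. Health department staff collect the month-12 survey, so obtaining it is easiest where the relationship with the worksite is still alive. The arms differ in the support given to those same staff, so the share and the kind of worksites lost could differ by arm. The contrast on a primary outcome would then mix the effect on implementation with an effect on who was measured. With no rule written down, the handling would be chosen after the data are seen.

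**Working it through.** **The plan's own figure.** The SAP states at least 80% power for a 6% difference. It gives no SD, intracluster correlation (ICC), significance level or attrition for this outcome, so the figure cannot be reproduced. It can be inverted. Assume two-sided 0.05, 20 departments per arm (SAP), 15 worksites each (Protocol 2.2, so 300 per arm), and 6% read as 6 points. The largest SD that gives 80% power is

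SD = 6 × √(300 / (2 × (1.96 + 0.84)² × DE)), with DE = 1 + 14 × ICC.

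This gives about 26 (ICC 0), 20 (ICC 0.05), 17 (ICC 0.10) and 13.5 (ICC 0.20). The documents do not say which applies.

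**Bias of the available-score contrast.** Let p be the share of worksites lost in an arm, and gap the mean score of retained worksites minus that of lost worksites. The retained mean exceeds the full mean by p × gap. Therefore

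bias (enhanced − standard) = p_E × gap_E − p_S × gap_S.

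If the gap is the same in both arms, this is gap × (p_E − p_S). All values below are assumed.

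| Gap E / S | Loss E / S | Bias (points) |
|---|---|---|
| 10 / 10 | 20% / 25% | 10 × (−0.05) = −0.5 |
| 15 / 15 | 20% / 30% | 15 × (−0.10) = −1.5 |
| 20 / 20 | 20% / 40% | 20 × (−0.20) = −4.0 |
| 15 / 15 | 30% / 20% | 15 × (+0.10) = +1.5 |
| 15 / 10 | 20% / 30% | 3 − 3 = 0 |
| 20 / 10 | 20% / 30% | 4 − 3 = +1 |

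The sign depends on which arm loses more and on how selective the loss is in each arm.

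**Check with an explicit stopping model.** Stopping was made logistic in the standardised score, with log-odds 0.5 to 2 per SD.

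- Standard arm losing 20%, 30% or 40% against 10% in the enhanced arm: bias −0.6 to −4.2 points at SD 12, −0.8 to −5.5 at SD 16, −0.9 to −6.9 at SD 20.
- Enhanced arm losing more (30% against 15%), SD 20: +1.4 to +3.4.
- Equal loss relative to each arm's own mean: no bias.

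**Simulated GEE.** 20 departments per arm, 15 worksites each, SD 20, ICC 0.05, exchangeable working correlation, robust SE, 600 runs.

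| Loss S / E | Related to score? | True 6: estimate, power | True 0: estimate, rejected |
|---|---|---|---|
| none | – | 6.0, 83% | 0.1, 7% |
| 30% / 10% | no | 6.0, 78% | 0.1, 6% |
| 30% / 30% | yes (log-odds 1 per SD) | 6.0, 81% | 0.0, 7% |
| 30% / 10% | yes (log-odds 1 per SD) | 2.6, 27% | −3.4, 38% |

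Only the combination of score-related and unequal loss does damage here.

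**What the baseline score can repair.** With SD 20, a true difference of 6, loss of 30% (standard) and 10% (enhanced) driven by baseline score alone, and a baseline to month-12 correlation of 0.6, the available-score difference is about 4.1. Baseline adjustment, or inverse-probability weighting on baseline, returns 6.0. If loss depends on the unseen month-12 score itself, neither repairs it fully.

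**Timing.** Section 2.2 expects recruitment over 24 months, and Section 5.1 gives a 24-month study period. A worksite that starts after month 12 of that period reaches its own month 12 after the period ends. Unless follow-up is extended, which the documents do not say, such worksites lack a score for administrative reasons.

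**The case against.** The strongest reply is that the loss is inferred. A reader might conclude that worksites which stop will not be surveyed. The documents do not say so. Section 5.1 sets no condition that a worksite still be active at month 12, and completing the programme is not defined as having a month-12 score. Text just before the re-survey sentence is redacted, the SAP is an excerpt from a grant proposal, and the N/A at 10.7 is weak evidence. This stands: the defect is a missing rule, not a stated exclusion.

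Three other tempting readings also fail.

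- *The GEE is valid only if scores are missing completely at random.* This is too strong. With a common gap the formula gives zero whenever losses are equal, and loss that depends only on modelled covariates does no harm.
- *Better retention in the enhanced arm means the analysis is biased against it.* This needs the gap to be equal in both arms. With gaps of 20 and 10 the bias favours the enhanced arm despite its better retention.
- *The bias is a quarter of the design difference.* This compares an assumed 1.5 points with 6. The SAP says 6% and does not state whether that is absolute points or a relative difference.

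Imputation also has limits. If stopping and missingness coincide, completion status cannot inform the imputation. Section 5.2 lists a count of completing worksites rather than a status for each, and does not list recruitment month. The fix allows for these points.

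**Conclusion.** The concern holds as a gap in the plan for a primary outcome. As written, the analysis is a linear GEE with no named covariates, fitted to whichever worksites have a month-12 score. It is in general biased if missingness is related to the score within arm and differs between arms. Both conditions are plausible here, and neither is established.

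Size and direction are unknown because no attrition rate is given. Under a common gap of 10 to 20 points and loss differences of 5 to 20 percentage points, the bias is about 0.5 to 4 points in absolute size, in either direction. The stopping models give up to about 7 points at SD 20 when 40% are lost in one arm and 10% in the other. These are assumption ranges, not estimates. The documents do not support calling this a penalty on the enhanced strategy.

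The plan should be changed before outcome data are examined. The trial design is not affected.

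**What to change.** 1. State that the month-12 Employer Assessment Survey is attempted at every worksite with a baseline survey whose month 12 falls within follow-up, whether or not the worksite is still active.
2. Treat worksites recruited too late to reach month 12 as administratively unobserved, and report them separately rather than mixing them with worksites that stopped.
3. Make the primary analysis a GEE adjusted for the baseline Employer Assessment score, after multilevel multiple imputation with health department as cluster. Use arm, baseline score and contacts with that worksite as predictors, plus recruitment timing if it is recorded per worksite.
4. Leave completion status out of the imputation model unless enough stopped worksites are surveyed to estimate its relation to the score.
5. Report missing month-12 scores by arm.
6. Add a not-at-random sensitivity analysis over a range of assumptions, one of them being that non-completers keep their baseline score.

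The cost is SAP wording, modest programming, a few more survey attempts by health department staff, and recording completion and recruitment date for each worksite. Baseline scores and contacts per worksite are already collected.

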developed and pilot-tested a distance-training model with success in several local health departments in Washington State.

**1.9 Supplements.** Check all boxes that apply, to identify Supplements you should complete and upload to the **Supporting Documents** SmartForm in **Zipline**.

*This section is here instead of at the end of the form to reduce the risk of duplicating information in this IRB Protocol form that you will need to provide in these Supplements.*

Check all That Apply	Type of Research	Supplement Name
	Department of Defense The research involves Department of Defense funding, facilities, data, or personnel.	ZIPLINE SUPPLEMENT: Department of Defense
	Department of Energy The research involves Department of Energy funding, facilities, data, or personnel.	ZIPLINE SUPPLEMENT: Department of Energy
	Drug, biologic, botanical, supplement Procedures involve the use of any drug, biologic, botanical or supplement, even if the item is not the focus of your research	ZIPLINE SUPPLEMENT: Drugs
	Emergency exception to informed consent Research that requires this special consent waiver for research involving more than minimal risk	ZIPLINE SUPPLEMENT: Exception from Informed Consent for Emergency Research (EFIC)
	Genomic data sharing Genomic data are being collected and will be deposited in an external database (such as the NIH dbGaP database) for sharing with other researchers, and you are asking the UW to provide the required certification or to ensure that the consent forms can be certified	ZIPLINE SUPPLEMENT: Genomic Data Sharing
	Medical device Procedures involve the use of any medical device, even if the device is not the focus of your research, except when the device is FDA-approved and is being used through a clinical facility in the manner for which it is approved	ZIPLINE SUPPLEMENT: Devices
	Multi-site study (You are asking the UW IRB to review one or more sites in a multi-site study.)	ZIPLINE SUPPLEMENT: Participating Site in Multi-Site Research

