**2.2 Inclusion and exclusion criteria.**

**a. Inclusion criteria.** Describe the specific criteria you will use to decide who will be included in your study from among interested or potential subjects. Define any technical terms in lay language.

Aim 1:

[redacted]

Aims 2/3:

Local health departments in the 50 states and District of Columbia will be eligible to participate in the randomized controlled trial. Additional eligibility criteria include willingness to support one or more staff members to participate in *Connect to Wellness* training and the project for two years, and to have these staff recruit 15 or more worksites for *Connect to Wellness* over 24 months. We will recommend to local health department staff that they focus on recruiting worksites with 20-200 employees (i.e. worksites with fewer resources for workplace health promotion, and for which the strongest evidence for the effectiveness of *Connect to Wellness* is present). The worksite representatives will need to be able to speak and read English, and be knowledgeable about health and wellness at the worksite (e.g. HR manager). We expect that representatives will be at least 18 years of age or older.

**b. Exclusion criteria.** Describe the specific criteria you will use to decide who will be excluded from your study from subjects who meet the inclusion criteria listed above. Define any technical terms in lay language.

Aim 1:

[redacted]

Aims 2/3:

Local health departments who are not able to support staff to participate in *Connect to Wellness* will be excluded from the study.

**2.3 Prisoners.** IRB approval is required in order to include prisoners in research, even when prisoners are not an intended target population.

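### The stated 80% power for 2.6 worksites per year is not reached from the SAP's own mean and SD under a two-sided 5% test, unless favourable assumptions that the SAP does not state are added

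*SAP*

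**What the plan says.** The SAP's power paragraph defines the endpoint: "Our first primary outcome is the number of worksites recruited by each LHD during the study period (24 months". It proposes 40 LHDs, 20 per arm, on the basis of Washington State pilot data, of which it reports: "The mean number of worksites recruited over a 12-month period was 8.4 (sd=4.4". It then claims: "The proposed design will have at least 80% power to detect a mean difference of 2.6 worksites per year between the two arms".

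For the analysis, the SAP says "we will use a generalized linear model with log link" with robust standard errors, "since we expect the number of worksites recruited to be overdispersed relative to the Poisson distribution". The question is worded in one direction ("To test whether LHDs in the enhanced arm recruit more worksites than LHDs in the standard arm"), but no one-sided test is declared.

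The SAP does not give alpha, sidedness, the power formula, the variance of the 24-month count, or the arm that 8.4 stands for. Protocol section 1.8b mentions only that the team "developed and pilot-tested a distance-training model with success in several local health departments in Washington State". It does not say whether those LHDs had one-on-one support. Protocol section 2.2a requires each LHD to be willing "to have these staff recruit 15 or more worksites for *Connect to Wellness* over 24 months".

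**The concern.** The pilot figures describe 12 months, the endpoint covers 24, and nothing in the SAP links the two. The link matters. If an LHD's second-year count is unrelated to its first, a second year halves the variance of the yearly rate. If strong recruiters stay strong, the second year adds much less. Putting the stated mean and SD through the usual formulas gives less than 80% on the natural readings.

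This sentence is the SAP's stated basis for 40 LHDs. If true power is lower, a non-significant first primary result could be misread as evidence that enhanced technical assistance does not add 2.6 worksites per year.

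**Working it through.** **Inputs.** From the SAP: n = 20 per arm; 12-month mean 8.4 and SD 4.4 (variance 19.36); difference 2.6 per year; 24-month count; log link. Assumed here: two-sided 5% (z = 1.960). Power = Φ(effect/SE − z).

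**1. Trying to reproduce 80%.** The SAP gives no formula, so the simplest comparison of means comes first. On 12-month data, SE = 4.4 × √(2/20) = 1.391 and 2.6/1.391 = 1.869, so power is 46%.

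**2. Means over 24 months.** With correlation rho between an LHD's two yearly counts, the SD of the yearly rate is 4.4 × √((1+rho)/2), and SE is that × √(2/20).

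| rho | SE | Power at 2.6, two-sided | Difference at 80% power |
|---|---|---|---|
| 0 | 0.984 | 75% | 2.76 |
| 0.1 | 1.032 | 71% | 2.89 |
| 0.57 | 1.231 | 56% | 3.45 |
| 1 | 1.391 | 46% | 3.90 |

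The value 0.57 is (19.36 − 8.4)/19.36, which treats all variance beyond Poisson as a lasting LHD effect. Two-sided 80% needs rho of about −0.11; no non-negative rho reaches it. A t reference lowers the rho = 0 figure to 73%.

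**3. Planned log-link model over 24 months.** With M = 2 × the yearly mean, SE² = the sum over arms of Var(M)/(20 × M²), and the effect is the log of the ratio of means. Variance models:
- Constant dispersion (no lasting LHD effect): Var = 2.305 × M, where 2.305 = 19.36/8.4.
- Negative binomial (persistent LHD effect): Var = M + 0.155 × M², where 0.155 = (19.36 − 8.4)/8.4².
- Constant SD: Var = 2 × 19.36 (rho = 0) to 4 × 19.36 (rho = 1).

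| 8.4 taken as | Yearly means | Negative binomial | Constant dispersion | Constant SD, rho 1 to 0 |
|---|---|---|---|---|
| overall mean | 7.1 v 9.7 | 56.4% | 74.9% | 44-73% |
| standard-arm mean | 8.4 v 11.0 | 46.4% | 68.9% | 45-74% |
| enhanced-arm mean | 5.8 v 8.4 | 68.9% | 81.5% | 44-72% |

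Worked example, overall mean with constant dispersion: log(9.7/7.1) = 0.312 and SE = 0.119, so 0.312/0.119 ≈ 2.63 and Φ(2.63 − 1.96) ≈ 75%. Simulation of the robust test agrees to within about 3 points. The larger simulated values come from the uncorrected robust z test, whose type I error is about 6.5%.

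**4. Routes to about 80%.**
- One-sided 5%: the means comparison gives 84% at rho = 0 and 80% at rho = 0.13. The log link gives 68-84% (overall), 59-79% (standard arm) and 79-89% (enhanced arm) from negative binomial to constant dispersion. With constant SD and rho = 0 it gives 82%, 83% and 82% (82.2%, 82.7%, 81.5%).
- Two-sided, with 8.4 as the enhanced-arm mean and variance proportional to the mean: 81.5% (79.5% with a t reference).
- Two-sided, with Poisson variance over 12 months: SE = √(2 × 8.4/20) = 0.917 and 2.6/0.917 = 2.84, so power is 81%. This replaces the reported variance of 19.36 by 8.4.

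**5. What a null result would show.** With 8.4 per year in both arms and an observed ratio of 1.0, the upper 95% limit is exp(1.96 × 0.117) = 1.26 under constant dispersion and exp(1.96 × 0.147) = 1.33 under the negative binomial. The target ratio is 11.0/8.4 = 1.31.

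**The case against.** The SAP text is an excerpt from a grant proposal, and the LHD-level pilot data behind it are not in the documents. The primary question is directional, and a one-sided 5% test gives up to 84% with 8.4 as the overall mean. The enhanced-arm reading reaches 81.5% two-sided, and no document excludes it. At the favourable end the gap is small: in the means comparison with uncorrelated years, an SD of 4.15 instead of 4.4 would give 80%. The low figures assume lasting LHD differences whose size nobody has reported. The ranges under negative binomial and constant dispersion are also not bounds, because constant SD lifts the standard-arm maximum from 69% to 74%.

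All of this stands, and it rules out the stronger reading. A reader might infer that the 80% is an arithmetic error, that true power is 46%, or that the sponsor used a Poisson variance by mistake. The documents support none of these. The inputs needed to call the figure wrong are missing, and the close match with a 12-month Poisson variance is only a coincidence of numbers as far as the documents show.

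Nor does the recruitment criterion settle which arm 8.4 describes. The enhanced-arm reading puts the standard arm at 2 × 5.8 = 11.6 worksites over 24 months, below 15, but the overall-mean reading gives 2 × 7.1 = 14.2, also below 15. The criterion concerns willingness and is not a forecast.

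What the objection does not rescue is the phrase claiming at least 80%. Each route to that level needs a choice the SAP does not state, or a variance that conflicts with its own SD and its expectation of overdispersion.

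**Conclusion.** The concern holds in this form. Under a two-sided 5% test, with 8.4 as the overall or standard-arm mean and SD 4.4, power at 2.6 per year is at most about 75%. It is about 44-56% if LHD differences persist, depending on the variance model. The shortfall from 80% is thus at least about 5 points on these readings, and its upper size cannot be fixed from the documents. The two-sided 5% level is an assumption of this review, as are the variance models and the between-year correlations.

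The consequence for a null result is also conditional. Under constant dispersion, an observed ratio of 1.0 would exclude the target ratio; under the negative binomial it would not. This should be fixed, because the sentence carries the sample-size justification. It does not show that 40 LHDs is the wrong number.

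**What to change.** Keep the 40 LHDs, the outcome and the model. Replace the 80% sentence with the power at 2.6 per year, or the difference detectable with 80% power, from one coherent calculation for the planned log-link model over 24 months. State alpha, sidedness, the mean assumed in each arm, and the 24-month variance or between-year correlation, taken from the pilot data. If a one-sided test was intended, or 8.4 as the enhanced-arm mean, say so and show that calculation.

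The figure should come from the sponsor's pilot data and not from the ranges above. As an example of scale: with a two-sided 5% test, SD 4.4 and uncorrelated years, a comparison of means gives about 75% power at 2.6 per year and 80% power at about 2.8 per year. Both become less favourable with any positive between-year correlation.

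Add that a non-significant result will be interpreted by its confidence interval against 2.6 worksites per year.

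The cost is SAP wording and one recalculation, with no extra LHDs. The downside is that the stated power will probably be less favourable.
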